2 STUDY OBJECTIVE(S)

2.1 Primary Objectives

- The primary objectives of the study are:
- To evaluate response rate per RECIST and iRECIST in patients treated in cohort A and in patients treated in cohort B.[19, 20] Tumor measurements will be in QIAC.
- To evaluate dose-limiting toxicities (DLT) in the first 6 patients enrolled to the study.

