In both Lead-in and Efficacy Stages, patients will be screened for study eligibility within 28 days before the first study drug dose after provision of written informed consent. Patients who are determined to be eligible, based on Screening assessments, will be enrolled in the study on Cycle (C)1, Day (D)1 (Baseline, before the first dose of BXCL701).

During treatment, patients will attend study center visits and have study evaluations performed as detailed in the Schedule of Assessments (Appendix A). All study visits will

be conducted on an outpatient basis but may be conducted on an inpatient basis per the investigator's judgement.

All patients must have pre-treatment (prior to study treatment dosing) imaging (computed tomography [CT] scan of chest/abdomen/pelvis or magnetic resonance imaging [MRI] for baseline tumor measurements, as well as bone scintigraphy [BS, if deemed necessary]). Patients with skin, subcutaneous or lymph node metastases may also have tumor evaluations (including measurements, with a ruler) by means of physical examination. Patients with a history of central nervous system (CNS) malignant involvement or CNS symptoms should have either CT or MRI imaging of the brain performed to assess active CNS malignancy.

Tumor measurements and disease response assessments (CT or MRI; BS) are also to be performed at the end of Cycle 3 (approximately 9 weeks after the first study treatment dose), and then approximately every 9 weeks thereafter until development of progressive disease (PD). Intervals can be shortened to 6 weeks if clinically necessary per treating physician. For patients with evidence of disease control (stable disease or better) at Week 27, tumor measurements and disease response assessments may be performed less frequently (approximately every 12 weeks) thereafter. Tumor measurements and disease response assessments also are to be performed at the End of Treatment (EOT) visit.

Study procedures are listed in Appendix A.

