7 DATA ANALYSIS AND STATISTICAL CONSIDERATIONS

This is a phase 2, single center, basket study of oral BXCL701 daily on days 1-14 in combination with intravenous PD1/PDL1 antibody on day1 of 21-day cycle in subjects with advanced and refractory malignancies. Lead-in cohort will enroll 6 patients. Only the 6 patients treated at the selected dose during safety lead-in will be assigned to Cohort A or B as appropriate. That is, if there is a dose de-escalation during safety lead-in, then the 6 patients treated at the higher dose will not be assigned to the phase II cohorts. Cohorts A and B will enroll 9 to 17 patients. Response assessments with CT and/or MRI will be done every 9 weeks (3 cycles) following RECIST and iRECIST criteria.[19, 20] Intervals can be shortened to 6 weeks (2 cycles) if clinically necessary per treating physician.

The study will follow the BOP2 design with the following operating characteristics.

Power: 0.80

Type I error: 0.05

P0:0.05**P1:**0.25

Each cohort will enroll 9 patients. If there is no complete (CR) or partial response (PR) in the first 9 patients the enrolment to that cohort will stop. If there ≥ 1 PR or CR in the first 9 patients the enrollment will continue to enroll total of 17 patients. PR or CR does not require confirmation. The treatment will be considered promising for further exploration if ≥ 3 CRs or PRs are observed in 17 patients. The expected **Sample Size** will range from 9 (if terminated after safety lead in) to 34 patients. Accounted for ~20% of patients not being evaluable for efficacy, the actual number of patients to be recruited for the trial will range from 11 to 42.

Scenarios (PA, PB)	Pr(reject H0 for cohort A)	Pr(reject H0 for cohort B)	Average sample size for cohort A	Average sample size for cohort B
(0.05,0.05)	0.046	0.046	12.0	12.0
(0.05,0.25)	0.046	0.813	12.0	16.4
(0.25,0.25)	0.813	0.813	16.4	16.4
(0.05,0.15)	0.046	0.455	12.0	15.1
(0.15,0.15)	0.455	0.455	15.1	15.1
(0.15,0.25)	0.455	0.813	15.1	16.4

Operating characteristics:

Note: PA is the response rate for cohort A, PB is the response rate for cohort B.

The Investigator is responsible for completing toxicity/efficacy summary reports and submitting them to the IND office Medical Affairs and Safety Group for review. These should be submitted as follows:

• Lead-In Stage:

After the first 6 evaluable patients, complete cycle 1 of study treatment. IND Office approval must be obtained prior to advancing to the efficacy stage.

• Efficacy Stage:

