Abbreviations: BP = blood pressure; CxDx = Cycle (number) Day (number); CBC = complete blood count; CT = computed tomography; ECOG = Eastern Cooperative Oncology Group; EOT = End of Treatment; FU = follow-up; HR = heart rate; MRI = magnetic resonance imaging; RR = respiratory rate.

a. After discontinuation of study drugs, patients will complete an EOT visit within 21 days after the last study drug dose.

Protocol 2019-0748 08 Apr 2022

- b. A Safety Follow-up Visit is to be conducted 30 days (±7 days) after the last dose of study drug and later if drug-related AEs have not resolved at that time. Thereafter, patients without documented disease progression (PD) will be followed every 90 days for disease assessments until documentation of PD. After documentation of PD, patients will be followed every 90 days for survival status; such follow-up will likely be conducted by telephone.
- c. Day 1 of Cycle 2 and all subsequent cycles will be 21 days (± 3 days) after the previous dose of study drug was administered.
- d. Tumor assessment must include cross-sectional imaging (MRI or CT scanning with intravenous contrast whenever possible) of the chest/abdomen/pelvis plus whole-body bone scan. Other body sites (e.g., neck) to be included as clinically indicated. Tumor assessment to be performed at Screening, C4D1 (±7 days), C7D1 (±7 days), C10D1 (±7 days), and Day 1 (±7 days) of every 3rd cycle thereafter and at EOT. Intervals for scans can be shortened to 6 weeks (e.g. C3D1, C5D1 etc.) if clinically necessary per treating physician.
- e. Serum chemistry to include: sodium (Na), potassium (K), chloride (Cl), bicarbonate, calcium (Ca), magnesium (Mg), phosphate, blood urea nitrogen (BUN)/creatinine (Cr), and lactate dehydrogenase (LDH).
- f. Liver function tests include aspartate aminotransferase, alanine aminotransferase, alkaline phosphatase, total bilirubin, and albumin.

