13.1 Measurability of tumor at baseline

At baseline, tumor lesions/lymph nodes will be categorized measurable or non-measurable as follows. Measurable lesions must be accurately measured in at least 1 dimension (longest diameter in the plane of the measurement to be recorded) with a minimum size of:

- 10 mm by CT scan (CT scan slice thickness no greater than 5 mm).
- 10 mm caliper measurement by clinical exam (lesions which cannot be accurately measured with calipers should be recorded as non-measurable).
- 20 mm by chest X-ray.

Malignant lymph nodes: To be considered pathologically enlarged and measurable, a lymph node must be ≥ 15 mm in short axis when assessed by CT scan (CT scan slice thickness recommended to be no greater than 5 mm). At baseline and in follow-up, only the short axis will be measured and followed.

Non-measurable lesions are all other lesions, including small lesions (longest diameter <10 mm or pathological lymph nodes with ≥ 10 to <15 mm short axis), as well as non-measurable lesions.

Response criteria	Evaluation of target lesions
CR	Disappearance of all target lesions. Any pathological lymph nodes (whether target or nontarget) must have reduction in short axis to <10 mm.
PR	At least a 30% decrease in the sum of diameters of target lesions, taking as reference the baseline sum diameters.
PD	At least a 20% increase in the sum of diameters of target lesions, taking as reference the smallest sum on study (this includes the baseline sum if that is the smallest on study). In addition to the relative increase of 20%, the sum must also demonstrate an absolute increase of at least 5 mm. (Note: the appearance of 1 or more new lesions is also considered progression).
SD	Neither sufficient shrinkage from the baseline study to qualify for PR nor sufficient increase to qualify for PD, taking as reference the smallest sum diameters while on study.

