13.4 Duration of response

The duration of overall response is measured from the time measurement criteria are first met for CR/PR (whichever is first recorded) until the first date that recurrent or PD is objectively documented (taking as reference for PD the smallest measurements recorded on study).

The duration of overall CR is measured from the time measurement criteria are first met for CR until the first date that recurrent disease is objectively documented.

Stable disease is measured from the start of the treatment until the criteria for progression are met, taking as reference the smallest sum on study (if the baseline sum is the smallest, this is the reference for calculation of PD).

14 APPENDIX C: RESPONSE EVALUATION CRITERIA IN SOLID TUMORS FOR IMMUNE-BASED THERAPIES (iRECIST)

Adopted from the bibliographic reference [19].

14.1 Comparison of response evaluation criteria in solid tumors (RECIST) 1.1 and modified response evaluation criteria in solid tumors for immune-based therapies (iRECIST)

	RECIST 1.1.	iRECIST
Definitions of	Measurable lesions are ≥ 10	No change from RECIST
measurable and non-	mm in diameter (≥ 15 mm for	1.1; however, new lesions
measurable disease;	nodal lesions); maximum of	are assessed as per
numbers and site of	5 lesions (2 per organ); all	RECIST 1.1 but are
target disease	other disease is considered	recorded separately on the
	non-target (must be ≥10 mm	case report form (but not
	in short axis for nodal	included in the sum of
	disease)	lesions for target lesions identified at baseline)
Complete response,	Cannot have met criteria for	Can have had iUPD (one
partial response, or	progression before complete	or more instances), but not
stable disease	response, partial response, or	iCPD, before iCR, iPR, or
	stable disease	iSD
Confirmation of	Only required for non-	As per RECIST 1.1
complete response or	randomized trials	
partial response		
Confirmation of stable	Not required	As per RECIST 1.1
disease		
New lesions	Result in progression;	Results in iUPD but iCPD
	recorded but not measured	is only
		assigned on the basis of
		this category if at next
		assessment additional new
		lesions appear or an
		increase in size of new
		lesions is seen ($\geq 5 \text{ mm for}$
		sum of new lesion target or
		any increase in new lesion non-target); the appearance
		of new lesions when none
		have previously been
		recorded, can also confirm
		iCPD

		-
Independent blinded	Recommended in some	Collection of scans (but not

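### Section 3 and Appendix A disagree on the baseline bone scan, so a first bone scan done on treatment could turn pre-existing bone disease into RECIST progression

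*Combined protocol and SAP*

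**What the plan says.** Three places deal with bone imaging.

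- **Section 3, baseline.** CT or MRI is required for everyone before treatment, "as well as bone scintigraphy [BS, if deemed necessary".
- **Section 3, on treatment.** The next paragraph reads "Tumor measurements and disease response assessments (CT or MRI; BS) are also to be performed at the end of Cycle 3", then about every 9 weeks. Here BS (bone scintigraphy) carries no condition.
- **Appendix A, note d.** "Tumor assessment must include cross-sectional imaging (MRI or CT scanning with intravenous contrast whenever possible) of the chest/abdomen/pelvis plus whole-body bone scan". The visits follow: "Tumor assessment to be performed at Screening, C4D1", then C7D1, C10D1, every third cycle after that, and end of treatment.

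In the Appendix A table, the Screening cells for CT/MRI and tumor assessment show a plain X, while the later-cycle and end-of-treatment cells show X with superscript d. The text was extracted from PDF and a superscript could have been lost, so this is supporting evidence at most.

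The primary objective is "To evaluate response rate per RECIST and iRECIST in patients treated in cohort A and in patients treated in cohort B". In Appendix B, "the appearance of 1 or more new lesions is also considered progression", whatever the target lesions show. In the Appendix C comparison, a RECIST response cannot follow progression, whereas a new lesion under iRECIST "Results in iUPD but iCPD" needs a further finding at the next assessment. No section says how to classify a lesion seen on a bone scan that has no baseline counterpart.

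**The concern.** Progression by new lesion is meaningful only if the same anatomy was examined at baseline with a comparable method. Section 3 does not secure this. A clinician may omit the baseline bone scan under its condition and then perform one at the end of Cycle 3 under its unconditional list. Disease in the skull or limbs that was present all along would then be seen for the first time.

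The timing matters. The first on-treatment assessment is usually the first chance to record a response, and Section 7 places the interim review after the first 9 evaluable patients in a cohort complete 9 weeks. A false RECIST progression at that scan removes the response then and bars it later. The cohort decisions turn on 0 versus 1 responder of 9 and 2 versus 3 of 17, so one reclassified patient can change a result.

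PFS is also exposed. If some patients have bone scans and others do not, progression is not ascertained in the same way across patients. The two versions of the primary endpoint can also disagree for the same patient.

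**Working it through.** **1. The text, read three ways.**

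| Reading | Baseline bone scan | On-treatment bone scan | Matched? |
|---|---|---|---|
| Note d in full | All patients | All patients | Yes |
| Section 3, condition carried forward | If needed | If needed | Largely |
| Section 3, literal | If needed | All patients | No |

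Following Section 3 at baseline and note d on treatment gives the same mismatch as the third row.

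**2. The plan's own design figures.** Inputs from Section 7: stop at 0 of 9, promising at 3 or more of 17, null rate 0.05, target rate 0.25. For response rate p,

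P(promising) = P(X17 ≥ 3) − P(X9 = 0) × P(X8 ≥ 3).

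At p = 0.25: 0.8363 − 0.0751 × 0.3215 = 0.8122; the plan states 0.813. The same rule gives 0.4559 at 0.15 (stated 0.455) and 0.0466 at 0.05 (stated 0.046). The plan's figures are reproduced to within 0.001.

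**3. How often one responder decides a cohort, at p = 0.25.**
- Exactly one responder in the first 9: 9 × 0.25 × 0.75^8 = 0.225. Losing that patient stops the cohort.
- Passing the interim and ending on exactly 3 of 17: P(X17 = 3) − P(X9 = 0) × P(X8 = 3) = 0.1893 − 0.0751 × 0.2076 = 0.174. Losing one responder reverses the conclusion.

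These two events overlap and should not be added. They show how sensitive the rule is, not how often misclassification happens.

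**4. Illustration of size.** The documents give no rate of bone disease, of omitted baseline scans or of misclassification. Assume that a share f of true responders is scored as RECIST progression before a response is recorded, so the observed rate is 0.25 × (1 − f).

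| f (assumed) | Observed rate | P(stop at 0 of 9) | Power |
|---|---|---|---|
| 0% | 0.250 | 0.075 | 0.812 |
| 2% | 0.245 | 0.080 | 0.800 |
| 5% | 0.2375 | 0.087 | 0.781 |
| 10% | 0.225 | 0.101 | 0.745 |
| 20% | 0.200 | 0.134 | 0.663 |

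**5. Direction.** This error only removes RECIST responses. It cannot raise the false-positive rate above the computed 0.0466, so the design value "Type I error: 0.05" is not threatened. The risk is to power and to the estimates.

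**The case against.** The strongest reply is that the problem needs a selective reading. Note d names Screening, so anyone who follows it has a baseline scan. Section 3 can also be read consistently, with its baseline condition carried forward to the on-treatment list. Both points are fair, and they limit the finding to a possibility. They do not remove it: Section 3 omits the condition on treatment, note d contradicts its baseline wording, and nothing says which text prevails.

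A reader might infer more than the documents support:

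- *That such patients are progressors on the primary endpoint outright.* This holds for RECIST 1.1 only. Under iRECIST the first call is unconfirmed progression, and a response may still follow.
- *That practice will differ between sites.* The trial is single-institution and tumor measurements are assigned to QIAC. Variation between clinicians in ordering scans remains possible, and the measurement arrangement does not state a rule for unmatched bone scans.
- *That affected patients must stop treatment.* Sections 5.7 and 8.5.1 let the investigator continue treatment past progression.
- *That power falls to about 0.66.* That needs one in five true responders to be lost. Each would need no baseline bone scan, an old lesion outside the CT field, a first bone scan on treatment, and no check against earlier imaging. At 2% lost, power is still 0.800, the design target.

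**Conclusion.** The inconsistency is real and should be corrected. Section 3 and note d disagree on whether the baseline bone scan is compulsory, and Section 3 taken literally permits unmatched bone imaging. The plan's own RECIST rules could then score old bone disease as progression and bar a later RECIST response. The error would lower the RECIST response count and shorten RECIST-based PFS; it does not inflate the type I error.

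The size cannot be derived from the documents. The power range of 0.800 to 0.663, for 2% to 20% of true responders lost, is an assumption and not an estimate. It also assumes that a cohort is judged on RECIST 1.1 responses. The documents do not support a claim that the bias will occur, or that it occurs when Appendix A is followed in full.

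**What to change.** Reconcile Section 3, the Appendix A table and note d into one rule under which baseline and on-treatment bone imaging match for each patient. Either option achieves this:

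1. a baseline bone scan for all patients, as note d already says; or
2. scheduled on-treatment bone scans only for patients who had a baseline scan.

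Then add two statements:

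- A lesion first seen on a bone scan with no baseline counterpart is not automatically new. It is checked against all available baseline imaging before it is classified.
- Response rate and PFS are reported twice, with such lesions counted as progression and as not progression.

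A rule that leaves such a lesion uncounted whenever no baseline image exists would be a poor substitute. Skull and limb lesions will often have no baseline image, so true bone progression there would be missed and the results would be biased favorably.

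The cost is wording plus two sensitivity analyses. Option 1 means more scans than Section 3 implies, in a trial open to patients from age 12. Under option 2, some asymptomatic bone progression is found later.

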received >70% of their BXCL701 in Cycle 1 (i.e., \geq 30 of 42 planned doses) with pembrolizumab dosed on Day 1 of Cycle 1 to be eligible for DLT assessment.

Toxicities will be assessed by the investigator using the National Cancer Institute Common Terminology Criteria for Adverse Events (NCI CTCAE), version 5. The relationship of an AE to combination therapy (i.e., attribution to BXCL701 and/or pembrolizumab) is to be assessed by the investigator using the criteria in the protocol (Section 5.3.1).

A DLT is defined as any of the following AEs occurring during Cycle 1, regardless of investigator attribution to study treatment, unless the AE can be clearly and incontrovertibly attributed to an extraneous cause (e.g., disease progression) by the Principal Investigator:

- Any Grade 4 laboratory abnormality, regardless of duration.
- Any Grade 3 laboratory abnormalities if associated with clinical symptoms regardless of duration
- Any Grade ≥3 non-hematologic AE, with the exceptions of Grade ≥3 nausea, vomiting, diarrhea, constipation, and fatigue, that resolves to Grade ≤1 within 72 hours with optimal medical management and/or supportive measures.
- Grade ≥3 thrombocytopenia with Grade >1 bleeding or requirement for platelet transfusion.
- Grade \geq 3 febrile neutropenia.
- Grade ≥ 3 fever.
- Grade ≥ 3 skin rash.
- Laboratory abnormalities meeting Hy's law criteria (aspartate aminotransferase [AST] or alanine aminotransferase [ALT] >3 × upper limit of normal [ULN] with concomitant total bilirubin >2 × ULN).
- Any toxicity resulting in \geq 30% held/skipped doses of BXCL701 during Cycle 1.
- Delay of Cycle 2 by ≥ 14 days due to toxicity.
- Any other significant toxicity considered by the investigator and supporter's medical representatives to be dose-limiting.

Efficacy Stage:

After assessment of the safety and confirmation of the BXCL701/pembrolizumab2 dose schedule to be used in the subsequent stage, the Efficacy Stage will begin. Eligible patients will receive oral BXCL701 daily on Days 1 to 14 of a 21-day cycle plus pembrolizumab 200 mg administered IV on Day 1 every 21 days.

Study Design Features (Both Stages):

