3.1 Justification for Dose

In a previously conducted multiple dose clinical study by Point Therapeutics with single agent BXCL701 (CA168-002), there was a dose dependent increase in plasma IL-6 in subjects receiving daily doses of BXCL701 from 0.3 to 1.2 mg when measured on Day 7. At doses ≥ 0.1 mg, pronounced inhibition of plasma CD26/DPP-IV activity to $\leq 20\%$ of baseline was apparent within 1 hour of dosing, and at doses of ≥ 0.3 mg, CD26/DPP-IV activity was almost completely inhibited (>95%) within 30 minutes of the first dose on Day 1. These pharmacologic data suggest that daily doses of 0.4 to 0.6 mg BXCL701 provide maximum pharmacodynamic inhibition, as measured by inhibition of plasma CD26/DPP-IV while also providing significant cytokine (IL-6 and G-CSF) upregulation over baseline.

BioXcel has considered the clinical AE profile of each therapeutic, BXCL701 and pembrolizumab, to clinically combine them. Based upon results from completed clinical trials, single agent BXCL701 is associated with AEs that are generally mild, manageable, and reversible. The most frequently observed AEs that appear to be characteristic of BXCL701 are edema/peripheral swelling, hypotension, dizziness, and hypovolemia. These events, including edema, tend to be manageable and reversible and usually resolve following a drug hold. The most common AEs associated with pembrolizumab include anemia, fatigue, hyperglycemia, hyponatremia, itching, cough, and nausea. A comparison of the safety profiles of BXCL701 and pembrolizumab does not indicate clinically significant overlapping potential toxicities. Given the lack of overlapping toxicities when the 2 agents are combined, it is expected that there will be no more toxicity than the sum of the individual toxicities observed at the maximum tolerated dose of each agent. Nonetheless, the starting dose for BXCL701 in combination with pembrolizumab is

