Clinical laboratory data are to be collected in this study, and toxicity trends will be analyzed utilizing objective toxicity criteria. Abnormal laboratory findings considered clinically significant by the investigator and outside the expected deviation for a patient with IPs should be reported as AEs. Wherever possible, a specific disease or syndrome rather than individual associated signs and symptoms should be identified by the investigator and recorded on the eCRF. Clinical syndromes associated with laboratory abnormalities are to be recorded as such (e.g., diabetes mellitus instead of hyperglycemia). However, if an observed or reported sign or symptom is not considered a component of a specific disease or syndrome by the investigator, it should be recorded as a separate AE on the eCRF.

PD should not be reported as an AE (see Section 5.7) unless the patient dies solely due to PD within 30 days of the last dose of IPs.

The relationship of each AE to each study drug (BXCL701 and/or pembrolizumab) will be evaluated by the investigator using the following definitions:

- Not related: The AE is clearly not related to the study drug(s). The AE can be explained to be likely related to other factors such as concomitant medications or the patient's clinical state.
- Possibly related: The AE may be related to the investigational agent(s). A plausible temporal sequence exists between the time of administration of the investigational product and the development of the AE, and it follows a known response pattern to the investigational product. The reaction may have been produced by the patient's clinical state or other concomitant therapies or interventions.
- Related: The AE is clearly related to the investigational agent(s). A plausible temporal sequence exists between the time of administration of the investigational product and the development of the AE, and it follows a known response pattern to the investigational product. The occurrence of this AE can be confirmed with a positive re-challenge test or supporting laboratory data.

The causality criteria of related and possibly related will be considered "related" to the study drug(s) for regulatory reporting requirements.

The investigator (or physician designee) is responsible for verifying and providing source documentation for all adverse events and assigning the attribution for all adverse events for subjects enrolled.

Attribution	Grade 1	Grade 2	Grade 3	Grade 4	Grade 5

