7.2 Clinical Laboratory Analyses

All clinical laboratory values will be listed individually and tabulated in a manner to identify safety concerns on a per-patient basis. Listing tables will be prepared for each laboratory measure and will be structured to permit review of the patient data as they progress on treatment. The tables will list the cycle of treatment, BXCL701 dose for Lead-in data, and the associated NCI CTCAE grade. Descriptive summary statistics will be generated per laboratory parameter.

Summary tables will be prepared to examine the distribution of these toxicities per cycle.

Graphic displays and shift tables may be provided to illustrate results over time on study. Assessment of cumulative toxicities may be made.

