- g. Serum will be collected if feasible predose (within 1 hour ± 30 minutes) and then 6 hours (± 1 hour) and 24 hours (±3 hours) postdose on C1D1. It will be also collected on C1D14 (± 1 days) and C2D1 (± 1 day) with the same daily schedule as C1D1 (pre-dose, 6 and 24 hours post-dose). The C1D1 and C2D1 24-hour samples will be collected prior to the D2 doses. C1D14 24-hour samples will be collected on C1D15. There will not be predose or 6-hour postdose serum collection on C2D14. Instead, there will be only one time 24-hour postdose collection on C2D15. Details about collection and processing are in the Laboratory Manual.
- h. Samples should be collected before dosing.
- i. If Cycle 1 Day 1 occurs <72 hours after Screening, physical examinations and clinical laboratory tests do not need to be repeated.
- j. Either BXCL701 or pembrolizumab may be administered first. However, on Cycle 1 Day 1, it is recommended that pembrolizumab will be administered first and that ≥1 hour should elapse before the administration of BXCL701 so that it will be easier to determine the relatedness of any AEs to study drug. It is s recommended to administer at least 1L of IV fluids if not medically contraindicated at Cycle 1 Day 1. It is at the investigator's discretion to provide IV hydration during in-person clinic visits beyond Cycle 1 Day 1.
- k. Whole blood will be collected on C1D1, C1D15 (±1 day), C2D1, C2D15 (±1 day), and at EOT for assessment of leukocytes by flow cytometry and other studies. Details about collection and processing are in the Laboratory Manual.
- 1. Archival tissue will be collected if available. Details about collection and processing are in the Laboratory Manual.
- m. Optional tumor biopsies will be obtained during screening and between Day 8 and Day 14 of cycle 2, and at EOT. Pre and post treatment biopsies will be mandatory if medically feasible in cohorts advancing to BOP2 stage. Details about collection and processing are in the Laboratory Manual.

Protocol 2019-0748 08 Apr 2022

- n. Pregnancy tests will be only for women with child bearing potential. Only whole blood will be collected for the pregnancy test that will be performed in the screening period (D -28 to D -1)
- o. Additional pregnancy tests will be performed D1 of each cycle only for women with child bearing potential. Whole blood or urine can be collected for the test.

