- p. Pregnancy test for the D1 of the 1st cycle can be skipped if the test for the screening period is performed close to the 1st cycle.
- q. Laboratory assessment for immune-related toxicities will be added as per patient's toxicity and as needed upon the investigator's discretion.
- r. Days 8 and 15 of Cycles 1 and 2 can have a window of \pm 2 days. These visits can be also preformed using the telehealth in case of unanticipated events such as COVID-19 pandemics if in agreement with applicable regulations.
- s. Details about collection and processing are in the Laboratory Manual.
- t. C1D5 visit has a window of -1 day and can happen on C1D4.
- u. T3, FT4 and TSH testing will performed at baseline, C4D1 (±7 days), C7D1 (±7 days), C10D1 (±7 days), and Day 1 (±7 days) of every 3rd cycle thereafter and at EOT.
- v. Hematology (CBC plus differential [5 part or auto-analyzer]), serum chemistry and liver function tests will not be performed on Days 8 and 15 after Cycle 4 (at Cycle 5 and beyond)

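### Section 3.1 names hyperglycemia as a common pembrolizumab adverse event, but the schedule requires no blood glucose, not even at baseline

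*Combined protocol and SAP*

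**What the plan says.** Section 3.1 (Justification for Dose) describes the partner drug's profile: "The most common AEs associated with pembrolizumab include anemia, fatigue, hyperglycemia, hyponatremia, itching, cough, and nausea".

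Appendix A, footnote e, defines serum chemistry analyte by analyte: "sodium (Na), potassium (K), chloride (Cl), bicarbonate, calcium (Ca), magnesium (Mg), phosphate, blood urea nitrogen (BUN)/creatinine (Cr), and lactate dehydrogenase (LDH". Glucose is not among them. Footnote q covers further tests: "Laboratory assessment for immune-related toxicities will be added as per patient's toxicity and as needed upon the investigator's discretion".

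Two footnotes change when chemistry is drawn. Footnote i can waive the Day 1 sample: "If Cycle 1 Day 1 occurs <72 hours after Screening, physical examinations and clinical laboratory tests do not need to be repeated". Footnote v thins later cycles: "serum chemistry and liver function tests will not be performed on Days 8 and 15 after Cycle 4 (at Cycle 5 and beyond".

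The analysis text assumes systematic laboratory data. Section 5.3.1 says "Clinical laboratory data are to be collected in this study, and toxicity trends will be analyzed utilizing objective toxicity criteria", and Section 7.2 says "All clinical laboratory values will be listed individually and tabulated in a manner to identify safety concerns on a per-patient basis", with CTCAE grades and summary statistics for each parameter. Among the Cycle 1 DLT criteria in Section 3 is "Any Grade 4 laboratory abnormality, regardless of duration".

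**The concern.** The plan expects hyperglycemia but leaves its detection to chance or individual judgment. If glucose is measured only when an investigator asks for it, asymptomatic cases can go unseen. The tabulated rate then reflects ordering habits as well as the treatment.

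The missing baseline adds a second problem. Diabetes is not an exclusion (Section 4.1.2 excludes only patients on gliptins). Steroids up to 10 mg prednisone-equivalent daily are allowed at entry, and corticosteroids are the planned treatment for immune-related events (Sections 5.1.1 and 6.5). A raised glucose on treatment could therefore come from prior disease, steroids or study drug. Section 5.3.1 requires attribution to each drug and counts worsening of a prior condition as an adverse event. Both judgments are weaker without a pre-treatment value.

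The Cycle 1 DLT rules are also touched, because no required glucose value feeds the laboratory criteria.

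**Working it through.** The plan states no figure for this point, so the check is to compare its sections and count scheduled samples.

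**Step 1. Does anything require a blood glucose?**

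| Source | What it requires | Blood glucose? |
|---|---|---|
| Footnote e, serum chemistry | 10 analytes (BUN and creatinine counted separately) | No |
| Footnote f, liver tests | 5 analytes | No |
| Hematology row | CBC with differential | No |
| Footnote u, thyroid | T3, FT4, TSH at baseline, every third cycle and EOT | No |
| Cytokine row | 12-cytokine panel in Cycle 1 | No |
| Urinalysis row | Screening, Day 1 of each cycle, EOT; components not specified | No (urine only) |
| Section 4.1.1, items 7 and 8 | Creatinine, albumin, bilirubin, AST/ALT, ANC, hemoglobin, platelets | No |
| Footnote q | Extra tests prompted by toxicity or at discretion | Not required |

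Required blood glucose measurements at screening, Cycle 1 Day 1, any later visit or EOT: 0.

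**Step 2. How are the other laboratory-defined events in Section 3.1 covered?** There are three. Anemia is covered by the CBC and hyponatremia by sodium in footnote e. Hyperglycemia has no test. Coverage is 2 of 3.

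**Step 3. How many scheduled chemistry draws could carry glucose?** From the serum chemistry row with footnotes i and v:

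- Baseline: screening (1) + Cycle 1 Day 1 (0 or 1) = 1 or 2.
- After the first dose: Cycle 1 Days 8 and 15 = 2; Cycles 2, 3 and 4, Days 1, 8 and 15 = 3 each. Total 2 + 3 + 3 + 3 = 11.
- Baseline plus post-dose through Cycle 4: 12 or 13.
- From Cycle 5: Day 1 of each cycle, plus EOT.

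The 11 is a maximum and applies to a patient treated through Cycle 4. Footnote r lets Days 8 and 15 of Cycles 1 and 2 (4 visits) be held by telehealth in unanticipated events. If all four went ahead without a draw, 11 − 4 = 7 would remain.

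**Step 4. Does urinalysis fill the gap in Cycle 1?** Scheduled urinalyses after Cycle 1 Day 1 and before Cycle 2 Day 1: 0. None falls in the DLT window after the first day.

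**Step 5. Which DLT criteria could be affected?** Grade 4 laboratory abnormalities count outright, and Grade 3 ones count if symptomatic. A separate criterion covers Grade 3 or higher non-hematologic adverse events, with listed exceptions, and could apply to hyperglycemia recorded as an adverse event. The documents do not show how CTCAE version 5 grades glucose, so the number of DLT calls this could change cannot be worked out.

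**The case against.** The strongest reply is that little depends on this. Overall safety is a secondary, descriptive objective in a single-arm study. No planned decision turns specifically on glucose, and hyperglycemia is already known for an approved partner drug. The Section 3.1 list sits in a dose rationale, and nothing in the plan promises a scheduled test for each event in it. That stands as an argument about weight. It does not dispute that the measurement is absent.

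Several provisions do help:

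- Footnote e sets a minimum, so glucose may be reported anyway.
- Footnote q applies to the whole laboratory block and says tests will be added when toxicity appears.
- Section 5.3.1 requires clinically significant abnormal results to be reported as adverse events, and uses hyperglycemia in its recording example.
- Daily safety calls on Days 3–4 and 6–14 of Cycle 1 give symptomatic events many chances to surface.
- Section 6.5 refers to the Prescribing Information for managing immune-mediated reactions.

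These make it less likely that a symptomatic case is missed. None of them requires a pre-treatment value or serial values in patients without symptoms. The Section 6.5 reference concerns dose modification and management, and its content is not in the documents.

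A further caution is that Section 5.1.1 announces supportive-care guidance that does not follow in the supplied text, and the abbreviation list defines diabetic ketoacidosis and type 1 diabetes. Guidance may exist elsewhere, so the finding is limited to the supplied text. Finally, this is a single-institution study, so the variation at issue is between investigators and not between sites.

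**Conclusion.** The concern holds. In the supplied protocol, hyperglycemia is an expected event with no required blood glucose at any time point: 0 required measurements, against 12 or 13 scheduled chemistry samples through Cycle 4 that could provide one (fewer with telehealth visits or early discontinuation). The tabulated rate may therefore be too low, and there is no required baseline for judging later values.

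The size of the under-count cannot be given, because the documents state no incidence and do not show how often glucose would be ordered anyway. If it is in practice reported with every chemistry panel and entered in the trial data, the loss is small. If it is ordered only for symptoms, asymptomatic cases are lost. The effect on DLT assessment is limited: symptoms could prompt testing, and only high-grade events count. The response endpoint and the 9/17-patient BOP2 rule are untouched. The change should be made because the gap concerns an event the protocol itself names and costs little to close.

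**What to change.** Insert glucose at the head of the analyte list in Appendix A, footnote e, and add it to the eCRF laboratory page. It is then reported at every serum chemistry time point. Screening, and Cycle 1 Day 1 where drawn, become the baseline, and Days 8 and 15 become the Cycle 1 on-treatment values. The tabulation in Section 7.2 then covers glucose without further change.

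The cost is one word in the footnote and one analyte in data entry. The test runs on serum already drawn, so no visit or blood draw is added. The downside is a few more low-grade hyperglycemia events on record, some of them from non-fasting samples.
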